6.7 PHARMACOKINETIC/PHARMACODYNAMIC ANALYSES

The PK analysis population is described in Section 6.1. The trial will evaluate the PK characteristics of satralizumab treatment by summary statistics and non-linear mixed effects analysis (population PK).

The serum concentration at each sampling timepoint will be described irrespective of whether patients receive acute relapse/rescue therapy, change background (baseline) treatment for NMOSD, miss a dosing or if the study drug administration is delayed. Individual and mean serum–concentration-versus-time curves will be plotted.

Descriptive statistics, such as geometric mean, geometric coefficient of variance and the 95% CI for the geometric mean for the serum satralizumab concentration, as well as arithmetic mean, standard deviation, median, minimum, and maximum on the measured serum satralizumab concentration, IL-6, sIL-6R, and CRP will be calculated by visit and per defined time window post-dose for the PK-PPS.

An exploratory analysis to identify any potential relationship among serum satralizumab concentration and PD (CRP, IL-6, sIL-6R) will be performed. These results will be described and reported in a separate analysis report.

Non-linear mixed effects analysis will be performed to analyze the satralizumab concentration–time data collected in the trial. The model to be used was previously developed on the basis of PK data from adult healthy volunteers and adult/adolescent patients with NMOSD (Satralizumab Simulation Report; available upon request). Further model development may be undertaken if needed in order to achieve a satisfactory description of the data, and the data from this study may be pooled with data from other studies with satralizumab. Population and individual PK and exposure parameters will be generated on the basis of the model. The results of the population PK analysis will be reported separately from the CSR.

Further details are described in a separate Data Analysis Plan.

6.8 IMMUNOGENICITY ANALYSES

The percentage of patients who have positive or negative ADA results will be tabulated. PK/PD, efficacy parameter and safety will be summarized by anti-drug antibody status.

The immunogenicity analysis population will consist of all patients with at least one ADA assessment. Patients will be grouped according to treatment received or, if no treatment is received prior to study discontinuation, according to treatment assigned.

The numbers and proportions of ADA-positive patients and ADA-negative patients at baseline (baseline prevalence) and after drug administration (post-baseline incidence) will be summarized by treatment group. When determining post-baseline incidence, patients are considered to be ADA positive if they are ADA negative or have missing data at baseline but develop an ADA response following study drug exposure (treatment-induced ADA response), or if they are ADA positive at baseline and the titer of one or more post-baseline samples is greater than fourfold of the titer of the baseline sample (treatment-boosted ADA response). Patients are considered to be ADA negative if they are ADA negative or have missing data at baseline and all post-baseline samples are negative, or if they are ADA positive at baseline but do not have any post-baseline samples that is greater than fourfold than the titer of the baseline sample (treatment unaffected).

The relationship between ADA status and safety, efficacy, PK, and biomarker endpoints may be analyzed and reported via descriptive statistics.

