2.5 IMMUNOGENICITY OBJECTIVES

The immunogenicity objective for this study is to evaluate the immune response to satralizumab on the basis of the following endpoint:

- Incidence of anti-drug antibodies (ADAs) from the first dose of satralizumab in Studies BN40898 or BN40900 (parent studies)

The exploratory immunogenicity objective for this study is to evaluate potential effects of ADAs on the basis of the following endpoint:

- Relationship between ADA status and efficacy, safety, and PK endpoints

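### Section 6.8 summarises PK/PD, efficacy and safety by ADA status but defines only an ever/never status with no onset date, so what precedes ADA can be counted as ADA positive; crude patient percentages and early-visit PK are the summaries exposed

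*Combined protocol and SAP*

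**What the plan says.** Section 2.5 makes this an exploratory objective: "The exploratory immunogenicity objective for this study is to evaluate potential effects of ADAs", with the endpoint "Relationship between ADA status and efficacy, safety, and PK endpoints".

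Section 6.8 then says "PK/PD, efficacy parameter and safety will be summarized by anti-drug antibody status". Later in the same section the relationship between ADA status and the other endpoints "may be analyzed and reported via descriptive statistics". One sentence commits to the summaries and the other leaves them optional.

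The only post-baseline ADA status is introduced by "When determining post-baseline incidence". Patients are positive if they are ADA "negative or have missing data at baseline but develop an ADA response following study drug exposure", or if they were positive at baseline and any later titre rises more than fourfold. A patient not positive at baseline is negative only if "all post-baseline samples are negative". Section 6.8 gives no onset date, time-varying status, landmark, or split of data before and after ADA.

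The summaries that could be broken down by this status are of different kinds:

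- **Patient percentages.** Section 6.6 tabulates the incidence of AEs, SAEs, selected AEs and withdrawals. Section 6.5 models rescue use as a yes/no outcome per patient.
- **Person-time measures.** ARR and Kaplan-Meier TFR (Section 6.5), and a rate per 100 patient-years in a sentence about adverse drug reactions (Section 6.6).
- **Concentrations.** Summarised by visit and post-dose window (Section 6.7).

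**The concern.** Ever/never status is fixed by what happens later in follow-up. A patient first positive in year 4 would carry the earlier relapses, AEs and troughs into the ADA-positive column. A patient with more samples also has more chances of a positive one and more time to have an event.

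Follow-up from first satralizumab dose does differ between patients. The treatment period ends on a common calendar date (Section 3.2). Patients randomised to placebo start satralizumab only in the open-label extension, and some patients entered the extension directly (Section 6.1.1). Parent-study patients who never roll over stay in the safety population (Section 6.1.3). ADA incidence is counted from the first parent-study dose (Section 2.5), and Appendix 1 schedules ADA samples about every 24 weeks in this study.

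At stake is whether a difference between ADA groups in these tables could be read as an effect of ADA. On some metrics it could not be told apart from an artefact of the grouping.

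**Working it through.** The documents give no ADA incidence, onset timing, parent-study follow-up lengths or target figure, so there is nothing to reproduce. The check asks what ever/never grouping shows when ADA has no effect at all.

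**Assumed inputs (none in the documents, except that the 24-week sampling interval follows Appendix 1).** Follow-up uniform over 1–8 years (also 3–8). AE rate 5 per 100 patient-years (also 15). First-relapse hazard 12 per 100 patient-years. ADA checked every 24 weeks. ADA onset either late (0.15 per year in all patients) or early (2 per year in half of them). Either nobody leaves at first relapse, or half do. Each scenario has 1,000,000 patients.

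**Mechanism by hand.** With AE rate λ and follow-up T, P(at least one AE) = 1 − exp(−λT). In the late-onset scenario mean follow-up is 5.24 years for ever-positive and 3.90 for never-positive patients:

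- ever: 1 − exp(−0.05 × 5.24) = 23.0%
- never: 1 − exp(−0.05 × 3.90) = 17.7%

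The simulation, which uses the whole follow-up distribution rather than its mean, gives 22.9% and 17.2%. The gap of 5.7 points comes from follow-up alone.

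**Results, ever-positive / never-positive, no ADA effect:**

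| Scenario | Mean follow-up (y) | Patients with an AE (%) | AEs per 100 PY | First relapses per 100 PY | KM relapse-free at 2 y (%) |
|---|---|---|---|---|---|
| Late onset, 1–8 y | 5.24 / 3.90 | 22.9 / 17.2 | 5.02 / 4.97 | 12.00 / 12.01 | 78.7 / 78.7 |
| Same, AE rate 15 | 5.24 / 3.89 | 52.6 / 41.9 | 15.00 / 15.01 | 12.00 / 12.03 | 78.7 / 78.6 |
| Late onset, 3–8 y | 5.77 / 5.19 | 24.8 / 22.6 | 5.00 / 4.98 | 12.03 / 12.00 | 78.7 / 78.6 |
| Early onset, 1–8 y | 4.55 / 4.46 | 19.9 / 19.6 | 5.00 / 5.02 | 12.02 / 11.98 | 78.6 / 78.7 |
| Late onset, half leave at first relapse | 4.90 / 3.27 | 21.3 / 14.7 | 4.98 / 5.02 | 9.33 / 14.49 | 85.4 / 74.2 |
| Early onset, half leave at first relapse | 4.11 / 3.74 | 18.2 / 16.6 | 5.01 / 5.02 | 10.80 / 13.17 | 82.1 / 75.6 |

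Reading the table:

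1. With late onset, 46% of ever-positive person-time and 52% of their first relapses fall before the first positive sample. With early onset the shares are 16% and 21%.
2. Crude percentages are inflated when onset is late, less so when follow-up is more even. Rescue use is counted from treated relapses, so the nearest proxy is patients with a relapse: 45.3% vs 35.7% in the first scenario.
3. Person-time measures do not move when only follow-up length differs.
4. If relapse ends follow-up, patients who relapse early leave before they can be found positive. The first-relapse rate ratio becomes 9.33/14.49, about 0.65 (about 0.8 with early onset), so ADA looks protective. Patients with a relapse reverse too: 38.0% vs 41.3% with late onset.

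**PK.** Suppose ADA truly halves concentration. At a visit where a share p of eventual positives has not yet converted, the apparent geometric mean ratio is 0.5^(1 − p):

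- p = 0.10: 0.54
- p = 0.45: 0.68
- p = 0.60: 0.76
- p = 0: the true 0.50

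Dilution is therefore greatest at early visits and fades as patients convert.

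**With time-varying status** (person-time and events before the first positive sample counted as ADA negative), four scenarios were rerun: late and early onset over 1–8 years, with and without leaving at relapse. The first-relapse rate ratio is 1.00 and the AE rate ratio 0.99–1.00 in each, which is the true null.

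**The case against.** The strongest reply is that Section 6.8 chooses no status for these summaries. The ever/never wording is tied to incidence, and Section 6 leaves detailed methods to an SAP. This stands in part: a reader might infer that the plan explicitly prescribes ever/never grouping for PK, efficacy and safety, and it does not. But no other post-baseline status is offered, so reuse is the natural reading, and nothing in the text prevents it.

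A reader might also infer that longer follow-up by itself makes ADA look harmful throughout. The documents do not support that. ARR, Kaplan-Meier TFR and rates per 100 patient-years are insensitive to follow-up length alone, and the direction can reverse. Section 4.6.1 foresees reassessing treatment after multiple or severe relapses, so relapse-related departure is possible, but its frequency is unknown.

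Nor is a single diluted PK ratio over all of a patient's samples supportable, because Section 6.7 summarises by visit. By-visit summaries limit the problem without removing it: at an early visit, a patient who converts years later still sits in the ADA-positive group.

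Two further objections stand in full. The analysis is exploratory and descriptive, and no test depends on it. A simple before/after split also has weaknesses: it treats transient positivity as permanent, and it puts early exposure mostly in the negative state, which confounds ADA with time on drug if event rates change over time.

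**Conclusion.** The concern holds in a limited form. As written, Section 6.8 leaves ADA status without a time anchor. Grouped by ever/never status, crude patient percentages (AEs, SAEs, selected AEs, rescue use) and early-visit concentrations would be biased under some patterns of ADA onset.

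On the assumed inputs, the spurious gap in patients with an AE at 5 per 100 patient-years is 5.7 points with late onset over 1–8 years, 2.2 points over 3–8 years, and 0.3 points with early onset. At an AE rate of 15 per 100 patient-years the late-onset gap over 1–8 years is 10.7 points. If half of patients leave at first relapse, first-relapse rates and Kaplan-Meier curves favour ADA positives. For PK, a real effect is hidden rather than exaggerated, mainly at visits before seroconversion.

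These sizes rest on the assumed ADA onset, event rates and follow-up. The documents fix only the unequal follow-up and the absence of an onset rule. The priority is low.

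**What to change.** In Section 6.8, or in the SAP to which it defers:

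- Keep ever/never status for ADA incidence only.
- Summarise each concentration and PD value by ADA status at that sample.
- For relapses and AEs, treat ADA status as time-varying from the first positive (or boosted) sample. Report events per patient-year in each state, by exposure year or adjusted for it; Section 6.5 already estimates ARR by exposure year.
- State how transient positivity is handled.
- Avoid crude patient percentages by ever-ADA status.
- Reconcile the two sentences in Section 6.8, one committing to these summaries and one making them optional.

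The cost is wording and modest programming, since sample and event dates are already collected. The downside is that ADA onset is known only to within the sampling interval of roughly 24 weeks, so some events near onset will be assigned to the wrong state.

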6.1.3 Safety Analysis Populations

All safety variables will be analyzed on the basis of the Safety Population (SAF). The SAF population will include all randomized or enrolled patients who have received at least one dose of study drug either during the parental studies or this study. It will encompass all patients from the parent studies, even if they do not participate in this study. Patients will be analyzed as treated for analysis purposes in the SAF.

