6.1.4 Pharmacokinetics Per-Protocol Set and Pharmacodynamics Analysis Population

The Pharmacokinetics Per-Protocol (PK-PPS) and immunogenicity (ADA) Set will include all patients in the SAF with at least one valid post-dose concentration or ADA titer result with a dosing record and sampling time. Pharmacodynamics variables (e.g., IL-6, sIL-6R, CRP) will be analyzed with use of the SAF population.

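### Sections 6.8 and 6.1.4 define incompatible ADA populations; 6.8 read literally counts patients without a post-dose sample as ADA negative, and it does not say which baseline it uses

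*Combined protocol and SAP*

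**What the plan says.** **Population.** Section 6.1.4 defines a combined PK per-protocol and immunogenicity set that "will include all patients in the SAF with at least one valid post-dose concentration or ADA titer result with a dosing record and sampling time". The SAF in 6.1.3 consists of "all randomized or enrolled patients who have received at least one dose of study drug either during the parental studies or this study". Section 6.8 gives a different rule: "The immunogenicity analysis population will consist of all patients with at least one ADA assessment". It also provides for patients who were never dosed, who are grouped, "if no treatment is received prior to study discontinuation, according to treatment assigned".

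**Classification.** Section 6.8 calls a patient ADA negative in two situations: the baseline is negative or missing and every later sample is negative, or the baseline is positive and no later titer exceeds four times the baseline titer (treatment unaffected). Neither asks for a minimum number of later samples.

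**Baseline.** Section 2.5 counts ADA incidence from the first satralizumab dose in either parent study. Section 6.8 classifies against a baseline that it does not identify. Appendix 1 schedules an ADA sample at the WN42349 baseline visit, when patients are already on satralizumab.

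**PD.** Section 6.1.4 assigns IL-6, sIL-6R and CRP to the SAF. Section 6.7 says that descriptive statistics for serum satralizumab and the same three variables "will be calculated by visit and per defined time window post-dose for the PK-PPS".

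**The concern.** ADA incidence is a named endpoint, and 6.8 also plans to summarise PK/PD, efficacy and safety by ADA status. A misclassified patient therefore affects the incidence table and every table split by ADA status.

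Three features put that classification in doubt. Two sections give different denominators. The negative rule can be met by a patient who has no post-dose sample and so no information on treatment-induced ADAs. And an unstated baseline lets two programmers place the same patient in opposite groups. The first two errors, and the WN42349 reading of the third, all push reported incidence downwards. The PD mismatch is a separate point of the same kind: two sections name different populations for the same summaries.

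**Working it through.** The documents state no ADA rate and no ADA calculation, so there is no figure of the plan's to reproduce. The check is to set the rules side by side and apply them literally.

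**Step 1: the two populations.**

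| Requirement | 6.1.4 | 6.8 |
|---|---|---|
| At least one dose | Yes, through the SAF | No; untreated patients have their own grouping rule |
| Post-dose result | Yes, concentration or ADA titer | No; any ADA assessment suffices |
| Dosing record and sampling time | Yes | Not mentioned |

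An untreated patient with an ADA sample is in the 6.8 population and cannot be in the 6.1.4 set. Going the other way, the word 'or' in 6.1.4 can admit a patient with a PK concentration and no ADA result, who is outside 6.8.

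**Step 2: the 6.8 rules applied to test patients under two baselines.** Titers are invented for the test.

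| Patient | Baseline before first satralizumab dose | Baseline at WN42349 visit |
|---|---|---|
| ADA arises in parent study, titer stays at 160 | Positive | Negative (treatment unaffected) |
| ADA arises in parent study, cleared before WN42349 | Positive | Negative |
| ADA arises in parent study at 40, rises to 320 in WN42349 (320 > 4 × 40 = 160) | Positive | Positive |
| ADA first appears in WN42349 | Positive | Positive |
| Pre-dose sample only, negative | Negative | Negative |
| Pre-dose sample only, positive | Negative | Negative |

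The last two rows follow because, with no later sample, it is true both that all later samples are negative and that none exceeds fourfold. These patients are in the 6.8 population. They are outside the 6.1.4 set unless they have a valid post-dose concentration.

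**Step 3: size of the dilution (assumed inputs).** Let I be the incidence among patients with a post-dose ADA result and m the share of the population without one. Reported incidence = I × (1 − m). With I = 30%: m = 1% gives 29.7%, 5% gives 28.5%, and 10% gives 27.0%.

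**Step 4: size of the baseline effect, only if the WN42349 visit were used (assumed inputs).** Take the planned 127 rollover patients (6.2). Let p be the share ADA positive at the WN42349 visit, all arising after the first dose; q the share of those later boosted more than fourfold; and r the share of the rest who newly convert.

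- Incidence from first dose = p + (1 − p)r
- Incidence from the WN42349 visit = pq + (1 − p)r
- Patients switched to negative = 127 × p(1 − q)

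With q from 0 to 20% and r from 2% to 5%:

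| p | From first dose | From WN42349 visit | Switched to negative |
|---|---|---|---|
| 10% | 11.8% to 14.5% | 1.8% to 6.5% | 10.2 to 12.7 |
| 50% | 51.0% to 52.5% | 1.0% to 12.5% | 50.8 to 63.5 |

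None of p, q, r, I or m comes from the documents.

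**The case against.** The strongest reply concerns the baseline. A reader might infer that 6.8 contradicts 2.5. It does not: 6.8 names no baseline, so this is an omission. Nor is the WN42349 reading clearly the intended one. Section 6.8 speaks of treatment groups and assigned treatment, which makes little sense in a single-arm study and fits an analysis pooled with the parent studies. Sections 6.5 and 6.10 tie change from baseline to randomization or first satralizumab dose. On that pooled reading, ADAs that arose in a parent study count as positive. Against this, the protocol usually says so when it means a parent-study baseline (4.5.6.2, 4.5.10, the footnote to Table 1), and its baseline visit in 3.1.1 is the WN42349 one. What stands is that the baseline is undefined, with an adverse consequence under one plausible reading.

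A reader might also infer that placebo-period samples of crossover patients would be counted as post-exposure. The text does not support this: 6.8 requires a treatment-induced response to follow study drug exposure and groups patients by treatment received.

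It can be said that the 'or' in 6.1.4 is meant respectively, concentration for PK and titer for ADA, and that nobody would tabulate a patient without a post-dose sample as negative. Both are sensible intentions, but neither is written. Section 6 defers detail to a SAP; the supplied text contains no further ADA rule, and a SAP would still have to choose between the two populations. The PD mismatch has no bearing on ADA classification, which is fair, but the two sections do differ.

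**Conclusion.** The point holds, as a minor one. Three parts rest on the text alone: 6.1.4 and 6.8 define ADA populations that cannot both be applied; 6.8 taken literally puts patients without a post-dose sample in the denominator as negative; and 6.1.4 and 6.7 name different populations for PD. The fourth is conditional: 6.8 does not identify its baseline, and only if it were taken as the WN42349 visit would stable or cleared parent-study ADAs be reported as negative.

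The size is unknown because no ADA rate is given. On the assumptions shown, the dilution is at most a few percentage points, whereas the wrong baseline could remove most of the positives. The documents do not support any particular figure, or a claim that the plan will in fact use the WN42349 baseline. No hypothesis test, error rate or sample size is touched; the effect is confined to descriptive immunogenicity, PD and by-ADA-status summaries.

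**What to change.** 1. In 6.1.4 and 6.8, use one ADA-evaluable population: patients with at least one satralizumab dose and at least one ADA result after it. Show patients without a post-dose ADA result as not evaluable. Adopting 6.1.4 unchanged would not be enough, because a PK concentration alone could qualify.
2. Define ADA baseline as the last available sample before the first satralizumab dose in the parent study, whether that dose fell in the double-blind or the OLE period. Keep the existing missing-baseline rule where there is no such sample. The parent-study sampling schedules are not supplied, so one cannot assume that every crossover patient has a sample just before the first satralizumab dose.
3. Label any incidence counted from the WN42349 baseline as a separate summary.
4. Name the same PD population in 6.1.4 and 6.7.

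The cost is a few sentences in the protocol or SAP and the matching analysis flags. No new visits or samples are needed.

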6.9 BIOMARKER ANALYSES

Although no formal statistical analysis of exploratory biomarkers will be performed, data may be analyzed in the context of this study and in aggregate with data from other studies.

6.10 HEALTH STATUS UTILITY ANALYSES

Change from baseline in EQ-5D-3L health utility index-based will be calculated at specified timepoints.

The EQ-5D-3L is a participant-answered questionnaire measuring 5 dimensions of mobility, self-care, usual activities, pain/discomfort, and anxiety/depression with 3 possible response categories: 1) no problems; 2) some problems; 3) severe problems. Therefore, EQ-5D-3L is able to represent 243 (3^5) distinct health states. These states may then be converted into a single index value by with use of the time trade-off (TTO) based tariff methods. The best possible answer would be (1,1,1,1,1) and the worst possible answer would be (3,3,3,3,3). A shift table will be used to evaluate the number and percentage of patients having a different post-baseline status when compared with their baseline status. The mean change in EQ-5D-3L score will be analyzed from randomization/first dose of satralizumab to every 24 weeks after the randomization/first dose of satralizumab visit.

